8.1.4. Definitions of Baseline and Change from Baseline

The period specific baseline will be defined as the last value recorded prior to the first dose of study drug in each period. If the date/time of the value is incomplete or missing, it will be excluded from the baseline calculation, unless the incomplete date/time indicates the value was recorded prior to the first dose.

Individual changes from baseline will be calculated by subtracting the individual subject's baseline value from the value at the timepoint. The mean change from period specific baseline will be defined as the mean of the individual changes from period specific baseline for all subjects.

See [Section 8.1.3](#) for more detail on handling repeat and unscheduled readings in the calculations. See [Section 8.1.2](#) for more detail on handling of triplicate readings in the calculations.

8.2. Subject Disposition and Population Assignment

Subject disposition and population assignment will be listed.

A summary table by treatment sequence will be provided, based on the all subjects population.

8.3. Screening Demographics

The screening demographics including age, sex, race, ethnicity, height, body weight, and body mass index will be listed.

A summary table by treatment sequence will be provided, based on the safety population.

8.4. Prior and Concomitant Medication

Prior medication will be defined as medication that ends prior to the first dose. Concomitant medication will be defined as medication that starts during or after the first dose or starts but does not end prior to the first dose.

Prior and concomitant medications will be coded using the World Health Organization Drug Dictionary Global, Format B3, Version September 2019 (or later if upversioned during the study). Prior and concomitant medications will be listed.

8.5. Pharmacokinetic Assessments

8.5.1. Pharmacokinetic Analysis

The following PK parameters will be determined where possible from the plasma concentrations of GDC-9545 using non-compartmental methods performed using Phoenix WinNonlin (Certara USA, Inc., Version 8.1 or higher):

Parameter	Definition
C_{max}	maximum observed concentration
t_{max}	time to maximum observed concentration
t_{last}	time of last quantifiable concentration
t_{lag}	time to first quantifiable concentration
AUC_{0-t}	area under the concentration-time curve calculated from Hour 0 to the last measurable concentration, calculated using the linear trapezoidal rule for increasing concentrations and the logarithmic rule for decreasing concentrations
$AUC_{0-\infty}$	area under the concentration-time curve from Hour 0 extrapolated to infinity, calculated using the formula: $AUC_{0-\infty} = AUC_{0-t} + (C_t/\lambda_z)$ where C_t is the last measurable concentration and λ_z is the apparent terminal elimination rate constant
$\%AUC_{extrap}$	percentage of area under the concentration-time curve that is due to extrapolation from the last measurable concentration to infinity
λ_z	apparent terminal elimination rate constant, where λ_z is the magnitude of the slope of the linear regression of the log concentration versus time profile during the terminal phase
$t_{1/2}$	apparent terminal elimination half-life (wherever possible), where $t_{1/2} = \text{natural log}(2)/\lambda_z$
CL/F	apparent total clearance, calculated as dose/ $AUC_{0-\infty}$
V_z/F	apparent volume of distribution during the terminal elimination phase, calculated as CL/F/ λ_z

Additional PK parameters may be determined where appropriate.

The PK analysis will, where possible, be carried out using actual postdose times recorded in the raw data. If actual times are missing, nominal times may be used with sponsor approval.

Concentrations will be used as supplied by the analytical laboratory for PK analysis. The units of concentration and resulting PK parameters, with amount or concentration in the unit, will be presented as they are received from the analytical laboratory.

The dose level of GDC-9545 will be converted to its free base equivalent for PK analysis if the analytical laboratory reports the free base concentration.

The C_{max} and t_{max} will be obtained directly from the plasma concentration-time profiles.

For multiple peaks, the highest postdose concentration will be reported as C_{max} . In the case that multiple peaks are of equal magnitude, the earliest t_{max} will be reported.

8.5.1.1. Criteria for Handling Concentrations Below the Limit of Quantification in Pharmacokinetic Analysis

Concentration values that are below the limit of quantification (BLQ) will be set to zero, with defined exceptions as follows;

- Any embedded BLQ value (between 2 quantifiable concentrations) and BLQ values following the last quantifiable concentration in a profile will be set to missing for the purposes of PK analysis.
- If there are late positive concentration values following 2 BLQ concentration values in the apparent terminal phase, these values will be evaluated. If these values are considered to be anomalous, they will be set to missing.
- If an entire concentration-time profile is BLQ, the profile will be excluded from the PK analysis.
- If a predose concentration is missing, these values may be set to zero.

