4 STUDY DESIGN

4.1 DESCRIPTION OF THE STUDY

This study will be an open-label, randomized, three-period, six-sequence crossover study of GDC-9545 administered at 30 mg in healthy females of non-childbearing potential to determine the relative bioavailability of the Phase 3 capsule formulation to the Phase 1 tablet formulation in the fasted state and the effect of food on the Phase 3 capsule formulation. Eighteen subjects will be enrolled in the study at a single study site to complete a minimum of 12 subjects. Study treatments are as follows:

- Treatment A:** 30-mg dose of GDC-9545 (three 10-mg tablets) administered orally with approximately 240 mL room temperature water after at least an 8-hour fast.
- Treatment B:** 30-mg dose of GDC-9545 (one 30-mg capsule) administered orally with approximately 240 mL room temperature water after at least an 8-hour fast.
- Treatment C:** 30-mg dose of GDC-9545 (one 30-mg capsule) administered orally with approximately 240 mL room temperature water within 30 minutes of eating a high-fat meal.

A summary of the sequences is presented in [Table 4-1](#).

[figure not shown]
Table 4-1 Three-Period, Six-Sequence Crossover Study Design

Sequence	Number of Subjects	Period 1 ^a	Period 2 ^a	Period 3 ^a
I	3	Treatment A	Treatment B	Treatment C
II	3	Treatment B	Treatment C	Treatment A
III	3	Treatment C	Treatment A	Treatment B
IV	3	Treatment A	Treatment C	Treatment B
V	3	Treatment B	Treatment A	Treatment C
VI	3	Treatment C	Treatment B	Treatment A

^a A minimum of 10 days between doses, with 7-day pharmacokinetic collection postdose and washout.
 Treatment A: 30-mg dose of GDC-9545 (three 10-mg tablets) administered orally with approximately 240 mL room temperature water after at least an 8-hour fast.
 Treatment B: 30-mg dose of GDC-9545 (one 30-mg capsule) administered orally with approximately 240 mL room temperature water after at least an 8-hour fast.
 Treatment C: 30-mg dose of GDC-9545 (one 30-mg capsule) administered orally with approximately 240 mL room temperature water within 30 minutes of eating a high-fat meal.

The study schematic is displayed in Figure 4-1.

Figure 4-1 Study Schematic

There will be a minimum 10-day washout between doses.

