4.2 RATIONALE FOR STUDY DESIGN

A crossover design will be used to reduce the residual variability as every subject acts as their own control. A single-dose, crossover design is the standard design to compare PK. Subjects will be randomized to one of six treatment sequences to minimize assignment bias.

This study is an open-label investigation because the PK parameters are believed not to be subject to bias. The crossover design further minimizes the effect of inter-subject variability. Blood sampling up to 168 hours postdose will allow the PK parameters of GDC-9545 to be adequately characterized based on prior data. The 10-day washout between GDC-9545 doses is considered sufficient to prevent carryover effects of the treatments based on the GDC-9545 geometric mean $t_{1/2}$ of 26.2 to 41.4 hours.

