ⁱ QuantiFERON[®] TB Gold test. If positive, subject will be excluded. Indeterminate results may be confirmed by repeat or by a purified protein derivative skin test. If a negative tuberculosis test has been documented within 3 months of Screening, no new test is needed.

^j Qualitative serum pregnancy test at Screening and urine pregnancy test at all other times. A positive urine pregnancy test will be confirmed with a serum pregnancy test. Follicle-stimulating hormone testing performed on postmenopausal females.

^k Prior to Period 1 dose.

^l For PK blood samples collected during the study, refer to [Table 7-2](#).

^m Sample collected prior to the GDC-9545 dose in Period 1.

Table 7-2 Pharmacokinetic Sampling Scheme

Study Day	PK Sampling Timepoints	Window (±)	Analyte (Matrix)
Day 1	Predose (0 Hour) any time prior to study drug administration	NA	GDC-9545 (Plasma)
	30 minutes	5 minutes	GDC-9545 (Plasma)
	1 hour	10 minutes	GDC-9545 (Plasma)
	1.5 hours	10 minutes	GDC-9545 (Plasma)
	2 hours	10 minutes	GDC-9545 (Plasma)
	2.5 hours	10 minutes	GDC-9545 (Plasma)
	3 hours	10 minutes	GDC-9545 (Plasma)
	4 hours	10 minutes	GDC-9545 (Plasma)
	5 hours	10 minutes	GDC-9545 (Plasma)
	6 hours	10 minutes	GDC-9545 (Plasma)
	8 hours	10 minutes	GDC-9545 (Plasma)
	12 hours	20 minutes	GDC-9545 (Plasma)
Day 2	24 hours	20 minutes	GDC-9545 (Plasma)
Day 3	48 hours	20 minutes	GDC-9545 (Plasma)
Day 4	72 hours	20 minutes	GDC-9545 (Plasma)
Day 5	96 hours	20 minutes	GDC-9545 (Plasma)
Day 6	120 hours	20 minutes	GDC-9545 (Plasma)
Day 7	144 hours	20 minutes	GDC-9545 (Plasma)
Day 8	168 hours	20 minutes	GDC-9545 (Plasma)

NA = not applicable; PK = pharmacokinetic.

Table 7-3 Clinical Laboratory and Safety Assessment Windows

Safety Assessment Timepoints ^a	Window (±)
Predose	45 minutes
0 to 24 hours postdose	15 minutes
Days 2 to 7	6 hours
Days 8 to 29	6 hours

^a Safety assessments may include vital signs, electrocardiograms, physical examinations, and clinical laboratory assessments. Not all safety assessments will be performed at each timepoint specified.

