Eligible subjects will be admitted to the study site on the day prior to GDC-9545 dosing (Check-in [Day -1]) of Period 1 to collect baseline data and familiarize the subjects with study procedures that will be used during the rest of the study. On Period 1 Day 1, subjects will be randomly assigned to one of six possible treatment sequences and the first dose of GDC-9545 in the assigned sequence will be administered in the morning. The washout period between doses will be a minimum of 10 days based on the GDC-9545 geometric mean $t_{1/2}$ of approximately 40 hours.

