8.5.1.3. Calculation of Area Under the Concentration-time Curve

The minimum requirement for the calculation of AUC will be the inclusion of at least 3 consecutive plasma concentrations above the lower limit of quantification, with at least one of these concentrations following C_{max} .

For any partial AUC determination (where applicable), nominal time will generally be used for the end of the interval. Actual times for partial AUC intervals may be used at the discretion of the Pharmacokineticist.

The AUC_{0-∞} values (and related parameters [CL/F and Vz/F]) where the percentage extrapolation is <30% will be reported. Any AUC_{0-∞} values (and related parameters) where the percentage extrapolation is ≥30% will be reported and flagged but excluded from statistics.

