8.5.1.4. Anomalous Values

If a value is considered to be anomalous due to being inconsistent with the expected PK profile, it may be appropriate to exclude this point from the PK analysis. However, the exclusion of data must have strong justification and will be documented in the raw data and CSR.

Embedded BLQ values may be considered anomalous depending on the route of administration and the characteristics of the drug.

Positive predose values >5% of C_{max} may be excluded from the summary statistics and statistical analysis at the discretion of the Pharmacokineticist.

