8.5.3. Pharmacokinetic Statistical Methodology

All PK concentrations and parameters will be listed.

Descriptive statistics (mean, median, minimum, maximum, SD, geometric mean, and geometric CV) will be calculated for all PK parameters for GDC-9545.

Summary tables, mean (+ SD) figures, overlaying individual figures, and individual figures by treatment and time postdose will be provided for plasma PK concentrations. All figures will be produced on both linear and semi-logarithmic scales. The +SD bars will only be displayed on the linear scale.

Summary tables by treatment will be provided for all PK parameters, with the exception of regression diagnostic PK parameters.

The PK parameters C_{max} , AUC_{0-t} , and $AUC_{0-\infty}$ for GDC-9545 will be analyzed to evaluate the relative bioavailability of GDC-9545 as a Phase 3 capsule formulation compared to a Phase 1 tablet formulation under fasted conditions and to assess the food effect on GDC-9545 PK for a Phase 3 capsule formulation. The mixed-effect analysis of variance model for three-period crossover design will be used for formulation comparison and fasted state and fed state comparison of capsule. The model will include sequence, formulation, and period as fixed effects and a random effect for subject within sequence. An unstructured covariance structure will be used; however, if this fails to converge, an alternative covariance structure may be applied.

Log transformed C_{max} , AUC_{0-t} , and $AUC_{0-\infty}$ values will be evaluated to estimate ratios of geometric mean values and the corresponding 90% confidence intervals (CIs).

The comparisons of interest are:

Relative bioavailability: Treatment B, capsule (Test) vs Treatment A, tablet (Reference)

Food effect on capsule: Treatment C, fed (Test) vs Treatment B, fasted (Reference)

An example of the SAS code that will be used (assuming formulation coding is 1 = Treatment A, 2 = Treatment B and 3 = Treatment C) is as follows:

```
proc mixed data=pk;
  by parcatln parcatl pkday paramn param;
  class trtan aperiod trtseqp usubjid;
  model log_pk = trtan aperiod trtseqp / residual ddfm=kr;
  random intercept / subject=usubjid(trtseqp) type=un;
```

```
estimate `Capsule - tablet' trtan -1 1 0/ cl alpha=0.1;  
estimate `fed - fasted' trtan 0 -1 1/ cl alpha=0.1;  
run;
```

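### t_lag is not tied to the current period's dose, so a quantifiable predose residual in Period 2 or 3 sets it to 0 and can empty the t_lag summary of information

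*SAP*

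**What the plan says.** The parameter table in SAP 8.5.1 includes t_lag, which is in neither the protocol's parameter list (9.2) nor the SAP's endpoint list (3.1). Its whole definition is "time to first quantifiable concentration". SAP 8.5.3 then sends it to the summary tables: "Summary tables by treatment will be provided for all PK parameters, with the exception of regression diagnostic PK parameters".

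A predose sample is taken in every period. Protocol Table 7-2 labels it "Predose (0 Hour) any time prior to study drug administration"; the first postdose sample is at 30 minutes. On spacing, SAP 4 says "The washout period between doses will be a minimum of 10 days".

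For positive predose values, SAP 8.5.1.4 has one rule. Values above 5% of Cmax "may be excluded from the summary statistics and statistical analysis at the discretion of the Pharmacokineticist". Nothing is said about smaller ones. SAP 8.5.1.1 sets BLQ values to zero, except that a BLQ value lying between two quantifiable ones becomes missing. Both documents leave the LLOQ without a value. SAP 8.5.1.3, for example, asks for "at least 3 consecutive plasma concentrations above the lower limit of quantification" and gives no figure.

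**The concern.** In a crossover, the first quantifiable concentration in a later period may be drug left from the previous dose. If the sample labelled 0 Hour is quantifiable, the definition is met at time 0 and t_lag is 0, however late absorption of the new dose begins. The SAP limits Cmax to postdose concentrations where a profile has several peaks, but puts no such limit on t_lag.

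The embedded-BLQ rule can add to this. If predose is just quantifiable and the 30-minute sample is BLQ, the sample that shows the delay is set to missing.

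At stake is a descriptive table. A delayed start of absorption is a plausible effect of a capsule shell or a high-fat meal, and those are the two comparisons the study is built on. Equal zero medians for the three treatments would look like absence of delay when they could simply be residual drug.

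**Working it through.** **Inputs.** Protocol Table 2-1, 30 mg (geometric mean, geometric CV): Cmax 177 ng/mL; AUC0-24 2110 and AUC0-∞ 5070 hr·ng/mL (CV 28.3% for AUC0-∞); half-life 41.4 h (CV 8.7%). The 10-mg row gives a half-life CV of 32.2%, used as a sensitivity value. Minimum interval: 10 days = 240 h. The LLOQ is assumed over a range.

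**Plan's own figure.** The half-life range in protocol 4.2, 26.2 to 41.4 h, matches Table 2-1. The washout is 240/41.4 = 5.8 half-lives (6.0 at 40 h).

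**Expected residual** (mono-exponential decline after 24 h):
- C24 = (5070 − 2110) × ln 2/41.4 = 49.6 ng/mL
- C168 = 49.6 × 2^(−144/41.4) = 4.4 ng/mL
- C240 = 49.6 × 2^(−216/41.4) = 1.33 ng/mL; 1.33/177 = 0.75% of Cmax
- Period 3 also carries the Period 1 dose: 1.33 + 49.6 × 2^(−456/41.4) = 1.36 ng/mL
- Threshold of the predose rule: 0.05 × 177 = 8.85 ng/mL, more than six times the residual

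**Share of Period 2 or 3 predose samples that are quantifiable at 240 h.** Simulated with lognormal spread in exposure (CV 28.3%) and half-life. Each cell gives half-life CV 8.7% / 32.2%. The columns differ in which quantity is held independent of half-life.

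| Assumed LLOQ (ng/mL) | AUC beyond 24 h | C24 |
|---|---|---|
| 0.1 | 100% / 98% | 100% / 96% |
| 0.5 | 99% / 82% | 99% / 77% |
| 1 | 78% / 62% | 75% / 59% |
| 2 | 12% / 29% | 16% / 35% |
| 4 | 0.1% / 4% | 0.3% / 13% |

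**Values forced to 0.** Each treatment opens two sequences of 3 subjects, so 6 of 18 profiles per treatment are from Period 1 and 12 are from Periods 2 and 3.
- LLOQ 0.5: 12 × 0.82 = 9.8 to 12 × 0.99 = 11.9 of 18 (9.2 at the lowest share, 77%). With 10 or more zeros the median of 18 is exactly 0; with 9 it lies midway between 0 and the smallest positive value.
- LLOQ 2: 12 × 0.12 = 1.4 to 12 × 0.35 = 4.2 of 18, so the median is not forced to 0.

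**Longer washout.** The point estimate falls to 0.89 ng/mL at 264 h, 0.60 at 288 h and 0.27 at 336 h. At 264 h and LLOQ 1, the quantifiable share falls to 37% to 46%.

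**Two simple repairs that fail.**
- *Postdose samples only.* A residual above the LLOQ is normally still above it at 0.5 h, so t_lag becomes 0.5 h regardless of the delay.
- *First postdose value above predose.* By 0.5 h the residual falls only by the factor 2^(−0.5/41.4) = 0.992. With nothing yet absorbed and independent assay errors of CV 5% to 15% (assumed), the 0.5 h value exceeds predose by chance in 45% to 48% of profiles.

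**The case against.** The strongest reply is that two conditions are needed and neither document establishes them: a quantifiable predose sample, and a predose sample that counts as the first quantifiable concentration. The LLOQ is not given. Sampling to 168 h, where about 4.4 ng/mL is expected, suggests a lower LLOQ, but the plan allows late BLQ values and does not require the 168 h sample to be quantifiable. SAP 8.5.1 also says the analysis uses actual postdose times where possible, so a pharmacokineticist might ignore the predose sample. This stands as a limit: the result is conditional. It does not supply the missing rule, and ignoring predose would only move the forced value to 0.5 h.

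A reader might infer three stronger things that the documents do not support:
- *That t_lag is zero in every Period 2 and 3 profile.* It is zero only where predose is quantifiable, and ten days is a minimum interval.
- *That an absorption delay would be hidden.* t_max is a listed endpoint with a median difference and 90% CI, and concentrations are tabulated and plotted by treatment with samples at 0.5, 1, 1.5, 2, 2.5 and 3 h. t_max mixes lag with absorption rate, so it does not replace t_lag, but a delay would still be visible.
- *That t_lag would compare periods instead of treatments.* Each treatment appears equally often in each period, so forced zeros should fall on A, B and C about alike. The loss is of information; it is not a bias towards one treatment.

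It is also fair that t_lag appears in no objective, endpoint list or model.

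**Conclusion.** The definition is incomplete for a crossover in which the protocol's own figures predict residual drug at the minimum washout, and no other SAP rule makes up for it. If the LLOQ is about 0.5 ng/mL or lower and intervals are close to 10 days, up to about 10 to 12 of 18 t_lag values per treatment would be 0 and the median about 0 for A, B and C alike. Around 1 ng/mL the median is borderline. At about 2 ng/mL or higher the effect is small. Longer intervals reduce it too, although a very sensitive assay would keep some of it.

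The harm is confined to an uninformative or misleading descriptive t_lag summary. The six Period 1 values per treatment are clean, and a residual of 0.75% of Cmax does not materially affect Cmax, AUC, t_max or the profiles.

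These sizes assume that tablet data from 6 patients carry over to healthy subjects and to the capsule, that decline is mono-exponential after 24 h, and that the predose sample is read as time 0.

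**What to change.** Add to SAP 8.5.1 that t_lag is derived from postdose samples only, with these cases:
- **Predose BLQ:** keep the present rule, the first quantifiable postdose sample.
- **Predose quantifiable:** choose one option before database lock. Either set t_lag to not calculated and summarise it only for profiles with BLQ predose, showing the number contributing per treatment; or use the first postdose sample that exceeds that period's predose value by a prespecified margin larger than assay error.

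State the LLOQ beside the rule so that its reach can be judged.

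No new data or procedures are needed. The first option costs t_lag values, possibly leaving little more than the six Period 1 profiles per treatment if the assay is sensitive. The second keeps more values but needs a justified margin, and slightly lengthens t_lag where early concentrations rise slowly.

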8.5.1.2. Criteria for the Calculation of an Apparent Terminal Elimination Half-life

8.5.1.2.1. Number of Data Points

At least 3 data points will be included in the regression analysis which preferably should not include C_{max} .

8.5.1.2.2. Goodness of Fit

When assessing terminal elimination phases, the adjusted coefficient for determination of exponential fit (R^2 adjusted) will be used as a measure of the goodness of fit of the data points to the determined line.

Regression-based parameters (ie, λ_z , $t_{1/2}$, $AUC_{0-\infty}$, CL/F , V_z/F) will only be calculated if the R^2 adjusted value of the regression line is ≥ 0.7 .

8.5.1.2.3. Period of Estimation

The time period used for the estimation of $t_{1/2}$ will be over at least 2 half-lives, where possible.

Where elimination half-life is estimated over a time period of less than 2 half-lives, it will be flagged in the data listings at the discretion of the Pharmacokineticist, and the robustness of the value should be discussed in the CSR.

8.5.1.3. Calculation of Area Under the Concentration-time Curve

The minimum requirement for the calculation of AUC will be the inclusion of at least 3 consecutive plasma concentrations above the lower limit of quantification, with at least one of these concentrations following C_{max} .

For any partial AUC determination (where applicable), nominal time will generally be used for the end of the interval. Actual times for partial AUC intervals may be used at the discretion of the Pharmacokineticist.

The AUC_{0-∞} values (and related parameters [CL/F and Vz/F]) where the percentage extrapolation is <30% will be reported. Any AUC_{0-∞} values (and related parameters) where the percentage extrapolation is ≥30% will be reported and flagged but excluded from statistics.

